6.2.2.6.3 Potential Drug-Induced Liver Injury

Abnormal values in AST and/or ALT levels concurrent with abnormal elevations in total bilirubin level that meet the criteria outlined below in the absence of other causes of liver injury are considered potential cases of DILI, and as potential Hy's Law cases, and should always be considered important medical events. If symptoms compatible with DILI precede knowledge of serum chemical test abnormalities, liver enzyme measurements should be made immediately, regardless of when the next visit or monitoring interval is scheduled. In some cases, symptoms may be an early sign of injury and although typically less sensitive than serum enzyme elevations, they may indicate a need for prompt serum testing. An increase in liver enzymes should be confirmed by a repeated test within 48 to 72 hours following the initial test, prior to reporting of a potential DILI event. Patients will continue to have weekly or biweekly liver enzyme measurements until resolution or levels return to baseline.

All occurrences of potential DILIs, meeting the defined criteria, must be reported as SAEs (see [Section 6.2.2.7.2](#) for reporting details).

Potential DILI is defined as:

1. ALT or AST elevation $> 3 \times$ ULN
AND
2. Total bilirubin $> 2 \times$ ULN, without initial findings of cholestasis (elevated serum alkaline phosphatase)
AND
3. No other immediately apparent possible causes of ALT or AST elevation and hyperbilirubinemia, including, but not limited to, viral hepatitis, pre-existing chronic or acute liver disease, or the administration of other drug(s) known to be hepatotoxic

The patient should return to the investigational site and be evaluated as soon as possible, include laboratory tests, detailed history, and physical assessment. In addition to repeating measurements of AST and ALT, laboratory tests should include albumin, CK, total bilirubin, direct and indirect bilirubin, GGT, prothrombin time (PT)/International Normalized Ratio (INR), and alkaline phosphatase. A detailed history, including relevant information, such as review of ethanol, acetaminophen, recreational drug and supplement consumption, family history, occupational exposure, sexual history, travel history, history of contact with a jaundiced person, surgery, blood transfusion, history of liver or allergic disease, and work exposure, should be collected. Further testing for acute hepatitis A, B, or C infection and liver imaging (e.g., biliary tract) may be warranted. All cases confirmed on repeat testing as meeting the laboratory criteria defined above, with no other cause for liver function test (LFT) abnormalities identified at the time should be considered potential Hy's Law cases irrespective of availability of all the results of the investigations performed to determine etiology of the abnormal LFTs. Such potential Hy's Law cases should be reported as SAEs.

Study drug discontinuation is considered if there is marked serum AST or ALT elevation or evidence of functional impairment (as indicated by rising bilirubin or INR, which represent substantial liver injury) that is related to study drug. Discontinuation of treatment should be considered if:

- ALT or AST > 8 × ULN
- ALT or AST > 5 × ULN for more than 2 weeks

Discontinuation of treatment must occur if:

- ALT or AST > 3 × ULN and (total bilirubin > 2 × ULN or INR > 1.5)
- ALT or AST > 3 × ULN with the appearance of fatigue, nausea, vomiting, right upper quadrant pain or tenderness, fever, rash, and/or eosinophilia (> 5%)

6.2.2.6.4 Malignancy

The identification of a malignancy event will be made by the study site and communicated to the sponsor or designee. AEs should be reported as serious per the criteria in [Section 6.2.2.5](#).

After the first dose of study drug, when there is a decision to biopsy a potentially malignant tumor, lymph node, or other tissue (with the exception of suspected basal cell/squamous cell), the Investigator and/or consultant(s) should contact the sponsor clinicians or designee to discuss the issue and any decisions as soon as possible. Basal cell carcinoma or squamous cell carcinoma of skin is not considered an AE of special interest.

6.2.2.6.5 Specific Infections

Any diagnosis or suggested diagnosis of opportunistic infections such as disseminated histoplasmosis, cryptococcosis, disseminated herpes simplex, disseminated tuberculosis, *Aspergillus* sp., *Candida albicans*, *Coccidioides immitis*, *Cryptococcus neoformans*, *Cytomegalovirus*, *Histoplasma capsulatum*, *Isospora belli*, or *Polyomavirus JC polyomavirus* will be recorded as AEs of special interest.

Cryptosporidiosis is also considered an AE of special interest. Patients will be evaluated for cryptosporidium in the stool at screening, and as clinically indicated (e.g., watery diarrhea) during the study. If a patient develops diarrhea during the study a stool sample must be provided to test for ova, parasites, and cryptosporidium.

6.2.2.7 Reporting of Adverse Events

AE reporting will be carried out in accordance with applicable local regulations, including regulatory agency and IRB reporting requirements.

Each AE is to be assessed to determine if it meets the criteria for an SAE. If an SAE occurs, expedited reporting will follow local and international regulations, as appropriate, and is further outlined in [Section 6.2.2.7.2](#).

6.2.2.7.1 Reporting of Pregnancy

As information is available, a pregnancy diagnosed during the study will be reported within 24 hours to the sponsor via the Pregnancy Notification and Outcome Form, including pregnancy in female patients who received study drug and female partners of male study patients who received study drug. The pregnancy should be followed to term and/or outcome and this outcome should also be reported to the sponsor via the Pregnancy Notification and Outcome Form. Pregnancy itself is not regarded as an AE or SAE unless there is complication.

In the case of a live birth, the structural integrity of the neonate can be assessed at the time of birth. In the event of a termination, the reason(s) for termination should be specified and, if clinically possible, the structural integrity of the terminated fetus should be assessed by gross visual inspection (unless pre-procedure test findings are conclusive for a congenital anomaly and the findings are reported).

If the outcome of the pregnancy meets the criteria for an AE or SAE (i.e., ectopic pregnancy, spontaneous abortion, intrauterine fetal demise, neonatal death, or congenital anomaly [in a live born, a terminated fetus, an intrauterine fetal demise, or a neonatal death]), the Investigator should follow the procedures for reporting SAEs.

Additional information about pregnancy outcomes that are reported as SAEs follows:

- Spontaneous abortion includes miscarriage and missed abortion
- Neonatal deaths that occur within 1 month of birth should be reported, without regard to causality, as SAEs. In addition, infant deaths after 1 month should be reported as serious adverse events when the Investigator assesses the neonatal death as related or possibly related to exposure to investigational product.

6.2.2.7.2 Reporting of Serious Adverse Events

The principal Investigator is responsible for providing notification to the sponsor of any SAE via the Safety Adverse Event Form, whether deemed study drug related or not, that a patient experiences during their participation in this study within 24 hours of becoming aware of the event.

If an SAE is fatal or life threatening, notification to the sponsor must be made aware immediately, irrespective of the extent of available AE information. This timeframe also applies to additional new information (follow-up) on previously forwarded SAE reports as well as to the initial and follow-up reporting of exposure during pregnancy and exposure via breastfeeding cases. In the rare event that the Investigator does not become aware of the occurrence of an SAE immediately (e.g., if an outpatient study patient initially seeks treatment elsewhere), the Investigator is to report the event within 24 hours after learning of it and document the time of his/her first awareness of the AE.

The principal Investigator will review each SAE and evaluate the intensity and the causal relationship of the event to the study drug. All SAEs will be recorded from the time of first dose of study drug through the safety follow-up period (up to Day 270).

SAEs occurring after the final follow-up visit and coming to the attention of the principal Investigator must be reported only if there is (in the opinion of the principal Investigator) reasonable causal relationship with the study drug.

As a minimum requirement, the initial notification should provide the following information:

- Study number
- Patient number
- Details of the SAE (verbatim details are sufficient for immediate notification)
- Criterion for classification as ‘serious’
- Causality assessment (which may be updated in a follow-up report when sufficient information is available to make this classification)

Initial reports of SAEs must be followed later with detailed descriptions, including clear photocopies of other documents as necessary (e.g., hospital reports, consultant reports, autopsy reports, etc), with the study patient’s personal identifiers removed. All relevant information obtained by the principal Investigator through review of these documents will be recorded and submitted to the sponsor within 24 hours of receipt of the information. If a new Safety Adverse Event Form is submitted, then the principal Investigator must sign and date the form. The sponsor may also request additional information on the SAE, or clarification of omitted or discrepant information from the initial notification, which the principal Investigator or an authorized delegate should submit to the sponsor within 24 hours of the request as possible.

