Blood samples were collected at every in-house study visit for BOS161721 concentration determinations. Blood samples were also collected for determination of IL-21 plasma levels (free and total). Safety was assessed based on the occurrence of treatment-emergent AEs, hepatic function abnormality, and acute and delayed hypersensitivity reactions. Other safety variables included ECGs, vital signs (blood pressure [BP], heart rate, and temperature), safety laboratory assessments, blood sampling for ADAs, total IgG and immunoglobulin M (IgM) levels, CD4+ count, and full and targeted physical examinations. Overall, there were no clinically significant findings from this study. Adverse events reported as related to the study drug, particularly infections, were expected for the compound, and there were no clinically relevant changes in laboratory and ECG results or vital signs. There was 1 serious adverse event (SAE; death due to pulmonary embolism) that occurred 127 days after a single administration of 240 mg SC dose of BOS161721. The causality of this single SAE was not attributed to study drug and further information can be found in the Investigator's Brochure. Final PK data from the SAD study demonstrates BOS161721 has a mean $t_{1/2}$ ranging from 80 to 87 days for doses of ≥ 30 mg in healthy subjects.

[figure not shown]

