1.2.5.9 Potential Risk to Fetal Development

No data on preclinical reproductive toxicity are available at the time of this study.

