3 STUDY PLAN

3.1 Study Design

This is a phase 1b/2 combined, randomized, multicenter, double-blind, placebo-controlled trial to study the clinical efficacy, safety, and PK of SC doses of BOS161721 in adult patients with moderately to severely active SLE. After successfully completing a screening phase, eligible patients will be randomized to a specified dose of BOS161721 or placebo. The dosing schedule will be monthly.

The trial will consist of 2 double-blinded portions: MAD phase 1b and POC phase 2. Patients may receive a total of 7 SC monthly doses of study drug on Days 0, 30, 60, 90, 120, 150, and 180, followed by safety follow-up visits at Days 210, 240, and 270.

SLE disease activity assessment data will be centrally reviewed by medical monitor and sponsor to ensure the scores are clinically meaningful and compliant with specific definition. The scope of responsibility includes, but is not limited to, review and confirmation of "A" and "B" BILAG system organ disease, confirmation of clinical components of the SLEDAI-2K score at screening and during the study, and cross-validation of the instruments used in this study to assess the disease activity. Further details on the content and methods of data reports by the medical monitor and sponsor will be outlined in the Medical Data Review Plan along with the processes and procedures that will be followed.

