4.7.2 Contraception

WOCBP must agree to follow instructions for method(s) of contraception for the duration of treatment with study drug plus 52 weeks, due to the mean terminal $\frac{1}{2}$ life of the study drug.

Men who are sexually active with WOCBP must agree to follow instructions for method(s) of contraception for the duration of treatment with study drug plus 52 weeks, due to the mean terminal $\frac{1}{2}$ life of the study drug.

Investigators shall counsel WOCBP and men who are sexually active with WOCBP on the importance of pregnancy prevention and the implications of an unexpected pregnancy. Investigators shall advise WOCBP and men who are sexually active with WOCBP on the use of highly effective methods of contraception. Highly effective methods of contraception have a failure rate of < 1% when used consistently and correctly.

- Patients must agree to either complete abstinence, defined as a complete avoidance of heterosexual activity, or the use of 2 methods of effective contraception from the following:
- Male condoms with spermicide
- Diaphragm with spermicide
- Cervical cap with spermicide
- Hormonal methods of contraception including combined oral contraceptive pills, vaginal ring, injectables, implants, patches and intrauterine devices (IUDs) such as Mirena® by patients who are WOCBP or a male patient's WOCBP partner. Women who are partner of men who are patients participating in the study may use hormone-based contraceptives as one of the acceptable methods of contraception since they will not be receiving study drug
- IUDs, such as ParaGard®
- Vasectomy
- Note: Women who are abstinent while participating in the study must continue to have pregnancy tests. Acceptable alternate methods of highly effective contraception must be discussed in the event that the patient chooses to forego complete abstinence

- Azoospermic men and WOCBP who are continuously not heterosexually active are exempt from contraceptive requirements. However, WOCBP must still undergo pregnancy testing

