5.5 Premature Discontinuation

While patients are encouraged to complete all study evaluations, they may withdraw from the study at any time and for any reason. Every effort will be made to determine why any patient withdraws from the study prematurely. If the patient is unreachable by telephone, a registered letter, at the minimum, should be sent to the patient requesting him/her to contact the clinic.

All patients who withdraw from the study with an ongoing AE or SAE must be followed until the end of study or until the event is resolved or deemed stable, respectively.

If a patient withdraws prematurely after dosing, an end of treatment (EOT) visit should be performed (Day 180) and a last follow-up visit 90 days after dosing should be scheduled (Day 270). Safety follow-up visit procedures based on the Schedule of Assessments (see [Section 5.4](#)).

Patient participation may be terminated prior to completing the study and the reason recorded as follows:

- AE/SAE
- Protocol deviation
- Lost to follow-up
- Patient withdraws consent at their own request
- Investigator decision
- Decision by the sponsor (other than AE/SAE, protocol deviation, or lost to follow-up)

Withdrawn patients may be replaced after discussion between the Investigator or designee and sponsor.

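### For completers, SAE reporting regardless of causality ends 90 days after the last dose, about one half-life, and the duty to report new pregnancies may end then too, although the half-life is used to require 52 weeks of contraception

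*Protocol*

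**What the plan says.** All references are to the current protocol (V7.0, Amendment 6).

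- **Dosing (Section 3.1):** "Patients may receive a total of 7 SC monthly doses of study drug on Days 0, 30, 60, 90, 120, 150, and 180". Safety follow-up visits are at Days 210, 240 and 270.
- **SAEs (Section 6.2.2.7.2):** all SAEs are recorded from first dose to Day 270, related or not. Those that occur after the final visit and reach the investigator "must be reported only if there is (in the opinion of the principal Investigator) reasonable causal relationship with the study drug". No end date is set for that related-only duty.
- **Pregnancy (Section 6.2.2.7.1):** "a pregnancy diagnosed during the study will be reported within 24 hours to the sponsor". Partners of male patients are included, and a reported pregnancy is followed to outcome.
- **Contraception (Section 4.7.2):** required "for the duration of treatment with study drug plus 52 weeks, due to the mean terminal" half-life. Section 1.2.5.9 adds: "No data on preclinical reproductive toxicity are available at the time of this study".
- **Half-life:** Section 1.2.2.3 gives the final single-dose figure as a mean "ranging from 80 to 87 days for doses of ≥ 30 mg in healthy subjects". Section 1.2.3 still cites 44 days from the Day-90 interim cut.
- **Precedent (Section 1.2.2.3):** the only SAE in the single-dose study was a "death due to pulmonary embolism) that occurred 127 days after a single administration of 240 mg SC dose of BOS161721", not attributed to drug.
- **Early withdrawal (Section 5.5):** "a last follow-up visit 90 days after dosing should be scheduled (Day 270"). Section 6.2.1.1 pairs the two in the same way for a patient stopped because of pregnancy.

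**The concern.** The protocol uses one property of the antibody, its long half-life, to restrict patients for a year after treatment. Yet it asks for SAE reports regardless of causality for only 90 days after a completer's last dose, and the duty to report a new pregnancy may end at the same point.

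After Day 270 the only filter is the investigator's view of causality, and that filter is strict. Section 6.2.2.4 offers two categories, and an event counts as related only if concurrent disease or other drugs cannot explain it. In lupus patients on background immunosuppression another explanation is usually available. Section 1.2.1 itself names thrombosis as the commonest cause of death in later disease, so a late pulmonary embolism could readily be judged unrelated. A randomized comparison is informative because it does not rely on such case-by-case judgments, and unattributed late events are the ones this rule leaves out.

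For pregnancy, a drug with no reproductive toxicity data may leave exposed pregnancies unreported during the period in which the protocol still requires contraception.

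**Working it through.** **Inputs.** Last dose Day 180 (Section 3.1); last visit and end of all-SAE recording Day 270 (Section 6.2.2.7.2); half-life 80 to 87 days final (Section 1.2.2.3) or 44 days interim (Section 1.2.3); death 127 days after a single dose (Section 1.2.2.3); contraception for 52 weeks = 364 days (Section 4.7.2), counted here from the last dose.

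**1. Interval.** 270 − 180 = 90 days, which reproduces the protocol's own 90 days. The ±3-day visit windows make it 84 to 96 days.

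**2. Half-lives elapsed and fraction remaining.** Half-lives = interval / t½; fraction = 0.5^(interval / t½), assuming first-order decay.

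| Days after last dose | t½ = 80 d | t½ = 87 d | t½ = 44 d (interim) |
|---|---|---|---|
| 90 | 1.125 half-lives, 45.9% | 1.03, 48.8% | 2.05, 24.2% |
| 127 | 1.59, 33.3% | 1.46, 36.4% | 2.89, 13.5% |
| 364 | 4.55, 4.3% | 4.18, 5.5% | 8.27, 0.3% |

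With the visit windows, the 80-to-87-day range at the last visit widens to 0.97 to 1.20 half-lives and 43.5% to 51.2% remaining.

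**3. The single-dose death placed in this trial.** Counted from a completer's last dose, it falls on Study Day 180 + 127 = 307, which is 127 − 90 = 37 days after the final visit. Judged unrelated, as it was, it would not have to be reported.

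**4. Pregnancy.** The contraception period ends on Study Day 180 + 364 = 544. On the individual definition in Section 3.5, a completer's study ends at the Day 270 visit. The difference is 544 − 270 = 274 days (about 39 weeks). The 90 days cover 90 / 364 = 25% of the contraception period.

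**5. Early withdrawal.** For a patient who stops after the Day 0 dose, 90 days after dosing is Day 90, but the text also says Day 270. These are 180 days apart. On the Day 270 reading the follow-up is 270/87 = 3.1 to 270/80 = 3.4 half-lives.

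**The case against.** Several stronger readings are tempting, and the protocol does not support them.

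- **That SAE reporting stops.** It narrows. Related SAEs remain reportable indefinitely, and Section 6.2.2.7 adds local regulatory requirements.
- **That an event on Study Day 127 is missed.** Study Day 127 lies inside the all-SAE window. The comparison works only when the 127 days are counted from the last dose.
- **That early withdrawals also leave at 90 days.** Sections 5.5 and 6.2.1.1 give two dates that differ for anyone who stops early. On the Day 270 reading, the actual precedent (one dose, death 127 days later) would be captured regardless of causality.
- **That late malignancies and opportunistic infections are lost.** Both are AEs of special interest. Section 6.2.2.7.3 requires reporting within 24 hours of awareness, with no end date or causality filter. Section 6.2.2.2 does limit AE collection to participation, so the text leaves their late coverage unclear.
- **That 274 days of pregnancies are certainly excluded.** Section 3.5 defines an individual and a global end of study. On the global reading, a pregnancy after a patient's own last visit stays reportable while the trial runs.
- **That completers leave with more drug on board than one 120 mg injection gives.** Assuming linear one-compartment decay and complete absorption, the amount at Day 270 is 120 × (1 − r⁷)/(1 − r) × 0.5^(90/t½), with r = 0.5^(30/t½). This gives 201 to 224 mg-equivalents at 80 to 87 days but about 74 at 44 days.

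It is also fair to say that 52 weeks is a contraception period and that nothing in the protocol makes it the standard for SAE reporting. The length of reporting is a design choice. What stands is that, for completers, the unconditional SAE window is short against the protocol's own final half-life, and that the pregnancy and early-withdrawal windows are not clearly defined.

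**Conclusion.** The point holds for patients who complete dosing. SAE reporting regardless of causality ends 90 days after the last dose. On the final half-life that is 1.03 to 1.13 half-lives with 46% to 49% of the drug level remaining; on the interim figure it is about 2 half-lives and 24%. The final figure deserves more weight, but both stand in the current text and should be reconciled. An unattributed death timed like the one in the single-dose study, counted from the last dose, would not have to be reported.

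For pregnancy, the wording may leave up to 274 days of the contraception period uncovered, depending on which end of study is meant. For early withdrawals, the defect shown is an ambiguous cut-off, not a proven 90-day one.

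The percentages assume first-order decay and that half-lives from healthy subjects carry over to lupus patients. This is a worthwhile, inexpensive improvement in safety information and does not affect the primary efficacy analysis.

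**What to change.** - **Section 6.2.2.7.1:** replace 'during the study' with a window from first dose to 52 weeks after the last dose, for patients and for partners of male patients.
- **Section 6.2.2.7.2:** require SAEs that come to the investigator's attention within the same 52 weeks to be reported regardless of causality, and keep the related-only rule after that. State that AEs of special interest (Section 6.2.2.7.3) follow the same window.
- **Sections 5.5 and 6.2.1.1:** reconcile 90 days after (the last) dosing with Day 270, so that the window for patients who stop early has one meaning.
- **Sections 1.2.2.3 and 1.2.3:** reconcile the 80-to-87-day and 44-day half-lives.

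The cost is protocol and consent wording, plus some later SAE and pregnancy forms. No extra visit or test is needed. The downside is that passive reports after the last visit will be incomplete. Some will arrive after database lock, because Section 8 runs the final analysis once POC safety follow-up is complete. For late-enrolled patients the gain for the DMC is therefore limited.
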